9.2.1. Demographic and clinical characteristics

Table 2. Variable definitions for demographic and clinical characteristics

Variable	Role	Time of measurement	Operational definition
Objective 1: demographic and clinical characteristics at first diagnosis of UC			
Age at initial diagnosis	Demographic and clinical characteristics	First diagnosis of UC	Derived using date of birth and date of initial UC diagnosis
Date of initial diagnosis	Demographic and clinical characteristics	First diagnosis of UC	As recorded: • Day/Month/Year of diagnosis
Stage at initial diagnosis	Demographic and clinical characteristics	First diagnosis of UC	As recorded: • Stage 0a • Stage 0is • Stage I • Stage II • Stage IIIA • Stage IIIB • Stage IVA • Stage IVB
Primary tumour site	Demographic and clinical characteristics	First diagnosis of UC	As recorded: • Bladder • Not-bladder

Sex	Demographic and clinical characteristics	First diagnosis of UC	As recorded: • Male • Female
-----	--	-----------------------	------------------------------------

Variable	Role	Time of measurement	Operational definition
			• Not known

Objective 1 (continued): demographic and clinical characteristics at diagnosis of locally advanced or metastatic UC

Age at diagnosis	Demographic and clinical characteristics	At locally advanced or metastatic UC diagnosis	Derived from date of birth and date of stage IV UC diagnosis
Date of locally advanced or metastatic UC diagnosis	Demographic and clinical characteristics	At locally advanced or metastatic UC diagnosis	As recorded: • Day/Month/Year of diagnosis
Stage of UC	Demographic and clinical characteristics	At locally advanced or metastatic UC diagnosis	As recorded • Stage III • Stage IVA • Stage IVB
Histology	Demographic and clinical characteristics	At locally advanced or metastatic UC diagnosis (or if not available, at initial diagnosis, where applicable)	As recorded: • Benign • Papillary urothelial neoplasm of low malignant potential • Malignant • Undifferentiated carcinoma

PD-L1 status	Demographic and clinical characteristics	At locally advanced or metastatic UC diagnosis (or if not available, at initial diagnosis, where applicable)	
 • PD-L1 test (present or not recorded) • Type of antibody testing used or not recorded • PD-L1 positive or negative or not recorded
ECOG performance status	Demographic and clinical characteristics	At locally advanced or metastatic UC diagnosis	As recorded (0-5)

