Objective 1 (continued): demographic and clinical characteristics at avelumab treatment initiation			
Age at avelumab initiation	Demographic and clinical characteristics	At avelumab treatment initiation	Derived from date of birth and date of avelumab initiation
ECOG performance status	Demographic and clinical characteristics	At avelumab treatment initiation	As recorded (0-5). For definitions of each category, see above

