### 5.2 SECONDARY OBJECTIVES:

1. To describe the clinical and demographic characteristics of the study population at first diagnosis of UC, diagnosis of locally advanced or metastatic disease and at avelumab treatment initiation.
2. To describe real-world progression-free survival (rwPFS) in the study population
3. To describe treatment characteristics of 1L anti-cancer therapies received prior to the initiation of avelumab as 1L maintenance therapy in the study population
4. To describe treatment patterns after initiation of avelumab as 1L maintenance therapy in the study population
5. To describe the AEs explicitly attributed to avelumab in the study population
6. To describe real-world all-cause healthcare resource burden associated with avelumab therapy in the study population

PFIZER CONFIDENTIAL

CT24-WI-GL03-RF03 0.2 *Non-Interventional Statistical Analysis Plan For Secondary Data Collection*  
*Study 01-Jun-2020*  
Page 12 of 34

[figure not shown]

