Age at date of locally advanced or metastatic cancer diagnosis	Demographic characteristic	At date of locally advanced or metastatic cancer diagnosis	Age (in years) at date of locally advanced or metastatic cancer diagnosis (eCRF Q11). Calculated as the number of years between date of birth (eCRF Q2) and date of locally advanced or metastatic diagnosis (eCRF Q10), rounded down to the nearest whole year of age.
Stage at locally advanced or metastatic diagnosis	Clinical characteristic	At date of locally advanced or metastatic cancer diagnosis	As recorded in eCRF Q13: 
 
• Stage IIIA
 
• Stage IIIB
 
• Stage IVA
 
• Stage IVB
 

Histology at locally advanced or metastatic diagnosis	Clinical characteristic	At date of locally advanced or metastatic cancer diagnosis (or if not available, at date of first diagnosis)	As recorded in eCRF Q14 (or eCRF Q8 for histology at date of first diagnosis): 
 
• Pure urothelial cancer (transitional cell carcinoma)
 
• Mixed urothelial with component of another pathology
 
• Other
 
• Not recorded
 

PD-L1 tumour assessment immune cell (IC) test result	Clinical characteristic	At date of locally advanced or metastatic cancer diagnosis (or if	Test result as recorded in eCRF Q23 (values range from 0-100; 'not recorded' will be treated as missing)

PFIZER CONFIDENTIAL

CT24-WI-GL03-RF03 0.2 *Non-Interventional Statistical Analysis Plan For Secondary Data Collection*  
*Study 01-Jun-2020*  
Page 19 of 34

		not available, at closest timepoint available)	
PD-L1 combined positive cells (CPC) test result	Clinical characteristic	At date of locally advanced or metastatic cancer diagnosis (or if not available, at closest timepoint available)	Test result as recorded in eCRF Q24 (values range from 0-100; 'not recorded' will be treated as missing)

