ECOG performance status at locally advanced or metastatic diagnosis	Clinical characteristic	At date of locally advanced or metastatic cancer diagnosis (or if not available, at date of first diagnosis)	
As recorded in eCRF Q19:
 
 
• 0 = Fully active, able to carry on all pre-disease performance without restriction
 
• 1 = Restricted in physically strenuous activity but ambulatory and able to carry out work of a light or sedentary nature, e.g., light housework, office work
 
• 2 = Ambulatory and capable of all self-care but unable to carry out any work activities. Up and about more than 50% of waking hours
 
• 3 = Capable of only limited self-care, confined to bed or chair more than 50% of waking hours
 
• 4 = Completely disabled. Cannot carry on any self-care. Totally confined to bed or chair
 
• Not recorded
 

De novo or newly relapsed	Clinical characteristic	At date of locally advanced or	
As recorded in eCRF Q15:
 
 
• De novo disease
 

PFIZER CONFIDENTIAL

CT24-WI-GL03-RF03 0.2 *Non-Interventional Statistical Analysis Plan For Secondary Data Collection*  
*Study 01-Jun-2020*  
 Page 20 of 34

		metastatic cancer diagnosis	
 
• Newly relapsed disease
 

Site of metastases at locally advanced or metastatic diagnosis	Clinical characteristic	At date of locally advanced or metastatic cancer diagnosis	
As recorded in eCRF Q16:
 
 
• Lymph nodes
 
• Bone
 
• Lung
 
• Liver
 
• Peritoneum
 
• Other
 
• Not recorded
 
 
Note that free text responses can be recorded under the 'other' option on the eCRF; these patients will be counted within the patient totals for 'other'. More than one site of metastases can be selected per patient, therefore percentage of total patients reporting each site will be shown, but percentages across all categories combined will not necessarily sum to 100%.

Time from first diagnosis to locally advanced or metastatic diagnosis	Clinical characteristic	At date of locally advanced or metastatic cancer diagnosis	Time (in months) between date of first diagnosis (eCRF Q5) and date of locally advanced or metastatic diagnosis (eCRF Q10), inclusive of both dates.

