## 9 HANDLING OF MISSING VALUES

No imputation of missing values will be carried out and the analyses will use a complete-case approach. The eCRF setup allows missing information for a number of variables to be included as ‘not recorded’ or ‘not stated’ options, and numbers of patients in these categories will be reported in descriptive statistics where appropriate. Descriptive statistics reported for continuous variables will include the numbers of patients with non-missing data per variable. For time-to-event analyses, the numbers of uncensored (at-risk) individuals will be reported at each timepoint.

For eCRF Q2 (‘Patient’s month and year of birth’), date of the month will not be recorded, and for eCRF Q10 (‘Date of locally advanced or metastatic UC diagnosis’), date of the month can be entered as unknown. For both of these variables, the 15th date of the month will be used to complete the full date as needed.

For eCRF Q4 (‘Date of initial diagnosis of urothelial carcinoma’), partial dates are allowed to be recorded where either date only is missing, or where date and month are both missing. Where only month and year are recorded, the date will be analysed as the 15th date of that month. Where only year is recorded, the date will be analysed as the 30th June of that year. Since this data is only used to calculate (i) age (in years) at first diagnosis, and (ii) time between initial diagnosis and locally advanced/metastatic diagnosis, this level of precision is expected to be sufficient.

PFIZER CONFIDENTIAL

CT24-WI-GL03-RF03 0.2 *Non-Interventional Statistical Analysis Plan For Secondary Data Collection*  
*Study 01-Jun-2020*  
Page 28 of 34

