### **Analysis of categorical variables**

Categorical variables will be described using frequency counts and percentages. Calculation of percentages will include a category for missing values where applicable for a given variable, therefore counts of missing observations will be included in the denominator and presented as a separate category. All percentages will be reported to one decimal place.

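### SAP Section 8 lets ECOG at advanced or metastatic diagnosis be taken from first diagnosis, with no time limit, flag or named source field, so the reported distribution can misdescribe the cohort

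*SAP*

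**What the plan says.** The ECOG row in SAP Section 8 is labelled as status at locally advanced or metastatic diagnosis. Its time of measurement reads "At date of locally advanced or metastatic cancer diagnosis (or if not available, at date of first diagnosis"). The source is given only as "As recorded in eCRF Q19", and the listed categories end with a not-recorded option.

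In the protocol (Section 9.2.1, Table 2) the matching row is measured at locally advanced or metastatic diagnosis and defined as "As recorded (0-5"), with no fallback. The histology and PD-L1 rows of the same table do allow the initial diagnosis to be used.

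On missing data, SAP Section 9 states: "No imputation of missing values will be carried out and the analyses will use a complete-case approach". For categorical variables, SAP Section 10.3 adds that "counts of missing observations will be included in the denominator and presented as a separate category".

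The protocol also has an ECOG row at avelumab initiation ("As recorded (0-5). For definitions of each category, see above"), and SAP Section 5.2 still promises characteristics "at first diagnosis of UC, diagnosis of locally advanced or metastatic disease and at avelumab treatment initiation". SAP Section 8 has no ECOG row at avelumab initiation, so the row discussed here is the only ECOG variable defined there.

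**The concern.** Performance status changes over time. Histology is a feature of the tumour, so an earlier value is a reasonable stand-in; an earlier ECOG value is not. Where a patient's two diagnosis dates coincide, the fallback can add nothing new. Every value that it does add therefore comes from an earlier date than the label states.

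The gap can be long. Relapsed patients are eligible, stage at first diagnosis runs from Stage 0a upward, and the interval between the two diagnoses is a reported variable with no maximum. SAP Section 9 even provides for first-diagnosis dates known only to the year.

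Two things are at stake in the baseline table, which serves a secondary objective. The ECOG distribution may describe an earlier and probably fitter state, and the not-recorded count may be smaller than it should be. Both documents also state an aim of comparing survival with the JB100 trial (Protocol Section 8, SAP Section 5), and a reader will look to the baseline table to judge how similar the cohorts are.

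**Working it through.** The plan gives no figure on this point to reproduce. The check is a comparison of the texts, followed by an illustration of possible size.

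**Texts side by side**

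| Variable at advanced diagnosis | Protocol Table 2 | SAP Section 8 | Fallback field named in SAP |
|---|---|---|---|
| Histology | Fallback to initial diagnosis | Fallback to first diagnosis | Yes: "As recorded in eCRF Q14 (or eCRF Q8 for histology at date of first diagnosis") |
| PD-L1 | Fallback to initial diagnosis | Fallback to closest available time point | One field per test (Q23, Q24) |
| ECOG | No fallback | Fallback to first diagnosis | None; only Q19 |

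The SAP therefore adds a fallback that the protocol does not have. It passes over any nearer ECOG value and goes straight to first diagnosis. It sets no window, asks for no flag, and does not say where a first-diagnosis ECOG value would be recorded.

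**Illustration of size**

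Inputs. N = 100 is the planned sample size (SAP Section 6.2). All other inputs are assumptions, because the documents give no ECOG distribution, missing rate or de novo share:

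- m = share of patients with ECOG missing at advanced diagnosis
- r = share of those with an earlier first diagnosis and an ECOG value from that date
- p_adv = 40%, the true ECOG 0 share at advanced diagnosis, taken as equal in patients with and without a recorded value
- p_first = 40% to 80%, the ECOG 0 share at first diagnosis among patients who are filled

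Formulas:

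- Patients filled = N × m × r
- ECOG 0 share among recorded, with fallback = [(1 − m) × p_adv + m × r × p_first] / [(1 − m) + m × r]
- Without fallback the share among recorded is p_adv = 40%

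Worked cases with p_first = 80%:

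- m = 20%, r = 60%: (0.80 × 0.40 + 0.12 × 0.80) / (0.80 + 0.12) = 0.416 / 0.92 = 45.2%, a shift of +5.2 points
- m = 40%, r = 60%: (0.60 × 0.40 + 0.24 × 0.80) / (0.60 + 0.24) = 0.432 / 0.84 = 51.4%, a shift of +11.4 points

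| m | r | Filled per 100 | Not recorded, without → with fallback | Shift, p_first = 40% | Shift, p_first = 60% | Shift, p_first = 80% |
|---|---|---|---|---|---|---|
| 5% | 30% | 1.5 | 5 → 3.5 | 0 | +0.3 | +0.6 |
| 20% | 60% | 12 | 20 → 8 | 0 | +2.6 | +5.2 |
| 40% | 60% | 24 | 40 → 16 | 0 | +5.7 | +11.4 |

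The shift has the sign of p_first − p_adv. It is zero if ECOG did not differ between the two dates, and would be negative if the filled patients had been less fit at first diagnosis.

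SAP Section 10.3 keeps missing values in the denominator, so the percentages actually printed would be on all patients. On that basis, with m = 20% and r = 60%, ECOG 0 goes from 0.80 × 0.40 = 32.0% to 32.0% + 12% × 0.40 = 36.8% when p_first = 40%, or to 32.0% + 12% × 0.80 = 41.6% when p_first = 80%. Part of that rise is simply patients moving out of the not-recorded category.

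**The case against.** **The fallback may never operate.** Neither document defines an ECOG variable at first diagnosis, and the ECOG row names only Q19, whereas the histology row names its fallback field. The phrase may have been carried over from the histology row. This stands, and it means that bias cannot be called demonstrated. It does not rescue the wording: either older values are entered in Q19, where the SAP gives no way to tell them apart, or the rule is inert. The text needs correcting in both cases.

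**The SAP may depart from the protocol.** Protocol Section 9.2 lets the SAP update operational definitions to suit available records, and Section 9.6 requires an amendment only for major changes to primary endpoints. This stands: the departure breaks no rule. Permission does not make an earlier measurement valid under a later label.

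**It does not contradict the no-imputation rule.** A reader might infer a flat contradiction with SAP Section 9. The documents do not settle that. The fallback sits in the time-of-measurement column, so it can be read as part of the variable's definition, as for histology and PD-L1, and the not-recorded category would still apply when neither value exists. The fallback fits poorly with Sections 9 and 10.3, but the point does not depend on calling it imputation.

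**It does not affect survival.** A reader might infer that rwOS is distorted. It is not: ECOG enters no planned survival analysis, and SAP Section 6.2 says that no formal comparisons are planned. Survival time also starts at avelumab initiation, after first-line chemotherapy, so ECOG at advanced diagnosis is not the natural baseline for reading it.

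**Some context will be reported.** Stage at first diagnosis, de novo or relapsed status, and time between diagnoses are all tabulated, and the table shells are a separate document not available here. These could show in aggregate that old values are possible, but nothing in Section 8 identifies which ECOG values were substituted.

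**Conclusion.** The point holds as a defect in a descriptive variable. The rule as written reports a time-varying measure under the wrong date, without limit or trace, in the only ECOG row of SAP Section 8.

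The tempting stronger statement is that the rule makes the cohort look fitter than it was. The documents do not support that as fact. Better status at an earlier stage is the probable direction, but nothing in the protocol or SAP fixes the sign or the size. De novo patients whose two diagnosis dates coincide are unaffected, and rwOS and rwPFS estimates stay the same.

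The illustrated shifts, up to about +5 points at 20% missing and about +11 at 40%, rest on the assumed 40% true ECOG 0 share, 40–80% at first diagnosis, and 60% of missing values being fillable. At 5% missing with 30% fillable the shift is at most +0.6 points. The understated missing count does not depend on direction: it follows whenever any value is filled.

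**What to change.** In the ECOG row of SAP Section 8, delete the parenthetical fallback to first diagnosis, leaving the time of measurement as the date of locally advanced or metastatic diagnosis. Count patients without a value at that time in the existing not-recorded category. This matches the protocol row, which has no fallback, and fits SAP Sections 9 and 10.3.

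The change is one phrase and needs no new data. Its cost is a larger not-recorded count, for example 20 rather than 8 per 100 in the 20% missing case above. The deletion does not supply the protocol's ECOG row at avelumab initiation, whose absence from SAP Section 8 has to be dealt with separately.

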9.6.3. Treatment patterns

In addition to the description of treatment characteristics, rwTTD and rwTTNT will be analysed using time to event analysis. Survival curves will be estimated using Kaplan-Meier methods and median (and IQR) time to event will be estimated with rwTTD and rwTTNT as endpoints. Table 1 describes the censoring endpoints. Healthcare resource utilisation

Healthcare resource burden (specifically number of all- cause hospitalisations, and duration of hospital stay, A&E admissions) will be reported. As reason for hospitalisation is harder to extract and subject to misclassification, only all-cause hospitalisation will be analysed.

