### **Follow-up and Censoring**

The follow-up period for participants will be from the index date to the earliest date of:

- Death (as recorded in eCRF Q35)
- Loss to follow up (as recorded in eCRF Q36)
- 24 months after the index date

For each participant, the censoring date used for the time-to-event analyses will be the earliest date of loss to follow up or 24 months after the index date, as recorded on the eCRF. Note that death is treated as an event in the time-to-event analyses, therefore not used as a censor point. For the time-to-progression variable only, the start date of 2L SACT will be used as an additional censoring point. Specific definitions of events and

PFIZER CONFIDENTIAL

CT24-WI-GL03-RF03 0.2 *Non-Interventional Statistical Analysis Plan For Secondary Data Collection*  
*Study 01-Jun-2020*  
Page 15 of 34

censoring for each time-to-event variable individually are provided in the relevant section of the table in [Section 8](#).

For a subset of the variables, data will be collected from medical records prior to the index date and recorded retrospectively in the eCRF. This look-back period will cover the period for each patient from the date (inclusive) of their first UC diagnosis (relating to diagnosis at any stage; as recorded on the eCRF Q5) to the day before the index date (inclusive). This look-back period applies to some clinical and demographic characteristics to be described for Objective 2, as well as some pre-avelumab treatment patterns to be analysed for Objective 4 (see [Section 8](#) for full details of each variable and the time period to be used for data collection).

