Adverse events	Patient outcome	From index date to date of censoring	The number of separate AEs recorded per patient (with explicit linkage in the medical notes to avelumab) will be calculated using data from eCRF Q39 (each reported event on the eCRF counts as a separate AE). This will be used to calculate the rate of events per patient per year of follow-up time
Objective 7: to describe healthcare resource burden associated with avelumab (table shell Table 2.6)			

PFIZER CONFIDENTIAL

CT24-WI-GL03-RF03 0.2 *Non-Interventional Statistical Analysis Plan For Secondary Data Collection*  
*Study 01-Jun-2020*  
 Page 26 of 34

Accident and Emergency visits	Healthcare resource burden indicator variable	From index date to date of censoring	The number of accident and emergency visits recorded per patient (each reported visit on the eCRF Q37 counts as a separate visit) will be used to calculate the rate of events per patient per year of follow-up time
Hospitalisations	Healthcare resource burden indicator variable	From index date to date of censoring	The number of hospital admissions recorded per patient (each reported visit on the eCRF Q38 counts as a separate visit) will be used to calculate the rate of events per patient per year of follow-up time
Duration of hospitalisation	Healthcare resource burden indicator variable	From index date to date of censoring	The total number of days duration of hospitalisation recorded per patient will be calculated as the sum of the duration of all separate hospitalisations reported per patient in eCRF Q38 (where the duration of each event is the number of days between the reported start and end date, inclusive of the start and end dates). This will then be used to calculate the number of days of hospitalisation per patient per year of follow-up time

PFIZER CONFIDENTIAL

CT24-WI-GL03-RF03 0.2 *Non-Interventional Statistical Analysis Plan For Secondary Data Collection*  
*Study 01-Jun-2020*  
 Page 27 of 34

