#### Analysis of continuous variables

All continuous variables will be described using the following statistics: number of observations, mean, standard deviation, median, minimum, and maximum values, first and third quartile (Q1 and Q3). The mean, median, Q1 and Q3 will be displayed to one decimal place. The standard deviation will be displayed to two decimal places.

The number of AEs, number of hospitalisations, duration of hospitalisation, and number of Accident & Emergency visits will each be used to calculate a rate per patient per year of follow-up time. This will be calculated as the total number of incident events (or total number of days hospitalisation) recorded per patient during the follow-up time divided by the total follow-up time (time at risk) per patient in years. All rate variables will be presented in the same way as for the other continuous variables.

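### Hospital days are summed record by record with no merging of touching or overlapping stays and no stated cut at the edges of follow-up, so a patient's total can exceed the days observed (minor)

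*SAP*

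**What the plan says.** SAP section 8, Objective 7, defines Duration of hospitalisation as "the sum of the duration of all separate hospitalisations reported per patient in eCRF Q38". For each stay, "the duration of each event is the number of days between the reported start and end date, inclusive of the start and end dates". The Hospitalisations row above it treats every entry as its own event: "each reported visit on the eCRF Q38 counts as a separate visit". Neither row has a step for records that share or overlap dates.

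A window is stated. The measurement period in these rows is "From index date to date of censoring". SAP section 10.3 (Analysis of continuous variables) takes the days "recorded per patient during the follow-up time divided by the total follow-up time (time at risk) per patient in years". Section 6.2 closes follow-up at the earliest of death, loss to follow-up or 24 months. Section 10.3 then summarises the per-patient rates like any other continuous variable, which includes the mean, minimum and maximum.

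Protocol section 9.2.3, Table 4, gives the unit as days and no counting convention.

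**The concern.** Inclusive counting is sound for one stay. Adding inclusive counts is sound only if the stays share no date. When a patient is transferred, or is discharged and readmitted on one date, that date belongs to both records and is counted twice. This is an error in calendar days and does not depend on preferring another unit.

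The second gap is at the edges of follow-up. The formula uses the reported dates, and no rule says to replace a start before the index date, or an end after follow-up closes, with the boundary date. The SAP has such a rule elsewhere: in the avelumab duration row, the censoring date stands in when no stop date comes first. Without a similar rule here, two programmers could derive different totals from the same records, and one of those totals would set days outside follow-up against a denominator confined to it.

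At stake are the hospital-days rates for the resource-use objective. Each rate is formed within a patient and then averaged, so a small excess in a patient with short follow-up is greatly magnified, and an impossible value would be printed as the maximum.

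**Working it through.** **Inputs.** From the documents: days per record = end − start + 1; simple sum over records; rate = days ÷ follow-up in years; about 100 patients. Neither document states a figure for hospital days, so there is nothing to reproduce. The dates below are assumed for illustration. Follow-up is counted inclusively and a year is 365.25 days.

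**Formulas.** SAP total = Σ(end − start + 1). Check = number of distinct calendar dates in hospital from the index date to the end of follow-up.

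| Assumed case | SAP total | Distinct days in follow-up | Excess |
|---|---|---|---|
| A. Separate stays, 1–6 Feb and 1–4 Apr | 6 + 4 = 10 | 10 | 0 |
| B. One episode, 1–15 Feb, entered as 1–6, 6–10 and 10–15 | 6 + 5 + 6 = 17 | 15 | 2 |
| C. In hospital for all of a 30-day follow-up, entered as days 1–15 and 15–30 | 15 + 16 = 31 | 30 | 1 |
| D. As C, one record | 30 | 30 | 0 |
| E. 27 Dec 2023–15 Jan 2024, follow-up 1 Jan 2022–31 Dec 2023 | 20 if not cut | 5 | 15 |
| F. 20 Dec 2021–3 Jan 2022, follow-up 1–10 Jan 2022 | 15 if not cut | 3 | 12 |

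**Rates.**

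- C: 31 ÷ 30 × 365.25 = 377 days per year, against 365 for distinct days.
- E (730 days of follow-up): 20 ÷ 730 × 365.25 = 10.0, against 5 ÷ 730 × 365.25 = 2.5.
- F: 15 ÷ 10 × 365.25 = 548, against 3 ÷ 10 × 365.25 = 110.

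Cases A and D show where the rule works: separate records inside follow-up give no excess. Case B shows that the excess from touching records is one day per shared date.

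**Effect on the mean.** One extra day adds 365.25 ÷ 10 = 36.5 days per year to the rate of a patient followed for 10 days, but only 365.25 ÷ 730 = 0.5 to that of a patient followed for 730 days. Averaged over 100 patients, these move the mean by 0.37 and 0.005 days per year. Case F alone would move it by (548 − 110) ÷ 100 = 4.4.

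**Denominator.** The SAP does not say whether follow-up days for these rates include both end dates. If they do not, case D also breaks: 30 ÷ 29 × 365.25 = 378.

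**The case against.** Much can be said for the plan.

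- **The unit.** A reader might infer that inclusive counting overstates every stay by at least one day. That holds only if nights are the target, and then the difference is exactly one per record. Both documents say days, and counting both end dates is the SAP's convention for its other intervals. For an isolated stay nothing is overstated. This objection stands.
- **The window.** A reader might infer that the plan ignores follow-up in the numerator. It does not: "recorded per patient during the follow-up time divided by the total follow-up time (time at risk) per patient in years" limits it, as does the measurement period in section 8. What is missing is narrower, namely the rule for cutting a stay that crosses the boundary. At the end of follow-up this cannot arise for patients who die, and the SAP expects more than 50 deaths among 100 patients by 24 months.
- **Day cases.** A reader might infer that same-day infusion visits will be counted as admissions. The documents are silent: the row concerns hospital admissions, emergency visits have their own question, and the eCRF and site instructions are not shown. A same-day entry would count as one admission and one day, but nothing shows that sites will make such entries.
- **Separate stays.** The word separate could mean one record per continuous stay. That would cover transfers if sites follow it, but not a true same-day discharge and readmission: those are two hospitalisations that share a date.
- **Rarity.** The extreme rates come from constructed cases with very short follow-up, and no formal comparison uses them. This also stands, and it limits severity.

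**Conclusion.** The point holds in a narrow form. As written, the formula counts a shared date more than once when records touch or overlap, and the SAP gives no explicit rule for cutting stays to the follow-up window that it states. Hospital days can therefore exceed days observed, and a per-patient rate can pass 365 days per year.

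The excess is one day per shared date for touching records, plus any days outside follow-up if stays are left uncut. The total effect cannot be computed, since the documents give no frequency or length of stays and no transfer rate. It is probably small: zero for isolated stays inside follow-up, and otherwise felt mainly in the mean and maximum through patients with short follow-up.

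The documents do not support a claim of general overstatement per stay, of a missing window, or of infusion visits being counted as admissions. Severity is minor. The outcome is descriptive and secondary, and real-world overall survival is unaffected.

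**What to change.** Reword the Duration of hospitalisation row in SAP section 8 along these lines: *hospital days are the number of distinct calendar dates on which the patient was in hospital between the index date and the end of follow-up, both included. Each Q38 interval is first cut to that window, and the union of the intervals is then taken, so that no date counts twice. A stay still open at the end of follow-up is closed on that date.* In section 10.3, state that follow-up days in the denominator also include both end dates.

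Leave the admission count as a separate variable and do not merge records for it, so that a genuine same-day readmission still counts as an admission. The unit remains days, as in the protocol.

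The cost is a short SAP edit and a few lines of code on dates already collected. The reported figure becomes slightly smaller, and no patient can have more hospital days than days observed.
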